• Assess whether BMS-986165 is superior to placebo at Week 16 in the treatment of subjects with moderate-to-severe plaque psoriasis	• sPGA 0/1 • PASI 75
Selected Secondary Endpoints	
• Assess whether BMS-986165 is superior to placebo over the first 16 weeks of treatment	• sPGA 0/1 [REDACTED] • PASI 90 • sPGA 0 • PASI 100 [REDACTED]
• Evaluate improvement in patient reported outcomes for BMS-986165 compared with placebo through Week 16	• Change from baseline in Psoriasis Symptoms and Signs Diary (PSSD) symptom score [REDACTED] [REDACTED] • PSSD symptom score of 0 (among subjects with a baseline PSSD symptom score ≥ 1) [REDACTED]

Overall Design:

This will be a 52 week, multicenter, randomized, double-blind, placebo-controlled study in subjects with stable moderate-to-severe plaque psoriasis. Subjects will undergo screening evaluations within 28 days prior to administration of study treatment to determine eligibility. Following the screening process, approximately 219 subjects will be randomized in a 2:1 ratio to either BMS-986165 6 mg QD or placebo, respectively.

Randomization should not occur until at least 8 days after the screening visit to allow collection of PSSD data during screening in order to calculate a baseline PSSD score. Randomization will be stratified by country (mainland China vs. non-mainland China) and previous biologic use (for psoriasis, psoriatic arthritis or other inflammatory diseases only; yes/no).

At Week 16, subjects randomized to placebo from screening through the Week 16 visit will be switched to BMS-986165 6 mg QD through Week 52 in a blinded manner, so that subjects who had been randomized to placebo will not know if they had been randomized to BMS-986165 or to

placebo post-screening. Subjects randomized to BMS-986165 6 mg QD will continue their current dose through Week 52.

At Week 24, a subject with sPGA ≥ 3 may be treated with restricted topical medications, such as topical high potency corticosteroids (WHO Classes I-V) but only at this time point and at the discretion of the investigator. This treatment may be continued through end of study.

Subjects who discontinue study treatment early are expected to remain in the study for continued follow-up until Week 52.

Subjects completing 52 weeks of treatment may be eligible to roll over to a separate long-term extension study and be treated with open-label BMS-986165 6 mg QD.

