7.2 Discontinuation from the Study

Subjects who request to discontinue study treatment will remain in the study and must continue to be followed for protocol specified follow-up procedures as specified in [Section 1.3](#). The only exception to this is when a subject specifically withdraws consent for any further contact with him/her or persons previously authorized by subject to provide this information.

- Subjects should notify the investigator of the decision to withdraw consent from future follow-up **in writing**, whenever possible.
- The withdrawal of consent should be explained in detail in the medical records by the investigator and entered on the appropriate CRF page.
- In the event that vital status (whether the subject is alive or dead) is being measured, publicly available information should be used to determine vital status only as appropriately directed in accordance with local law.
- If the subject withdraws consent for disclosure of future information, the Sponsor may retain and continue to use any data collected before such a withdrawal of consent.

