7.3 Lost to Follow-up

- All reasonable efforts must be made to locate subjects to determine and report their ongoing status. This includes follow-up with persons authorized by the subject.
- Lost to follow-up is defined by the inability to reach the subject after a minimum of **three** documented phone calls, faxes, or emails as well as lack of response by subject to one registered mail letter. All attempts should be documented in the subject's medical records.
- If it is determined that the subject has died, the site will use permissible local methods to obtain date and cause of death.
- If investigator's use of third-party representative to assist in the follow-up portion of the study has been included in the subject's informed consent, then the investigator may use a Sponsor-retained third-party representative to assist site staff with obtaining subject's contact information or other public vital status data necessary to complete the follow-up portion of the study.
- The site staff and representative will consult publicly available sources, such as public health registries and databases, in order to obtain updated contact information.
- If after all attempts, the subject remains lost to follow-up, then the last known alive date as determined by the investigator should be reported and documented in the subject's medical records.

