8.2.2 Time Period and Frequency for Collecting AE and SAE Information

The collection of nonserious AE information should begin at initiation of study treatment until discharge from the study (ie, final study visit for a given subject), at the timepoints specified in the Schedule of Activities ([Section 1.3](#)).

The Reference Safety Information in Sections 5.6.1 and 5.6.2 of the IB should be used to determine expectedness of SAEs for expedited reporting. Following the subject's written consent to participate in the study, all SAEs, whether related or not related to study drug, must be collected, including those thought to be associated with protocol-specified procedures.

All SAEs must be collected from the date of subject's written consent until 30 days after the final dose of the study drug or subject's participation in the study if the last scheduled visit occurs at a later time. Monitoring for SAEs will occur at every study visit.

- The investigator must report any SAE that occurs after these time periods and that is believed to be related to study drug or protocol-specified procedure. Medical occurrences that begin before the start of study treatment but after obtaining informed consent will be recorded on the appropriate section of the CRF.
- All SAEs will be recorded and reported to Sponsor or designee within 24 hours, as indicated in [APPENDIX 3](#).
- The investigator will submit any updated SAE data to the sponsor within 24 hours of this being available.

Investigators are not obligated to actively seek AEs or SAEs in former study subjects; however, if the investigator learns of any SAE, including a death, at any time after a subject has been discharged from the study, and he/she considers the event reasonably related to the study treatment or study participation, the investigator must promptly notify the Sponsor.

The method of evaluating and assessing causality of AEs and SAEs and the procedures for completing and reporting/transmitting SAE reports are provided in [APPENDIX 3](#).

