4.2 Safety

The safety outcomes include the following:

- Adverse events (AEs)
 - Treatment-emergent adverse events (TEAEs) – defined as:
 - AEs which occur after the first dose of study treatment through 30 days after the final dose of the study treatment;
 - Treatment-emergent adverse events of interest (AEIs) for the following events:
 - Skin-related AEs
 - Infection AEs, including influenza
 - Creatine kinase (CK) elevation (evaluated as lab toxicity grade 2 or higher)
 - Malignancy
 - SAEs
 - Deaths
- Clinical laboratory parameters

Sponsor: Bristol-Myers Squibb

Protocol no: IM011065

- Absolute and change from baseline values
- Laboratory abnormalities (as determined by Controlled Terminology Criteria for Adverse Events [CTCAE v5.0] grading) presented as the worst postbaseline toxicity group
- Shifts from baseline to maximum postbaseline value
- Potential drug induced liver injury (DILI) is defined as a subject who meets the following criteria:
 - 1) ALT or AST elevation >3 times ULN

AND

 - 2) Total bilirubin >2 times ULN, without initial findings of cholestasis (elevated serum alkaline phosphatase)

AND

 - 3) No other immediately apparent possible causes of liver function test elevation and hyperbilirubinemia, including, but not limited to, viral hepatitis, preexisting chronic or acute liver disease, or the administration of other drug(s) known to be hepatotoxic.
- ALT or AST elevation >5 times ULN
- Vital signs
 - Absolute and change from baseline values
 - Marked abnormalities defined by the below categories:
 - Heart rate:
 - Value > 100 and change from baseline > 30
 - Value < 55 and change from baseline < -15
 - Systolic blood pressure:
 - Value > 140 and change from baseline > 20
 - Value < 90 and change from baseline < -20
 - Diastolic blood pressure:
 - Value > 90 and change from baseline > 10
 - Value < 55 and change from baseline < -10
- Electrocardiograms (ECGs)
 - Absolute and change from baseline values
 - Marked abnormalities defined by the below categories:
 - QT interval corrected using Fridericia's formula (QTcF):

Sponsor: Bristol-Myers Squibb
Protocol no: IM011065

- 450 -< 480 msec
- 480 -< 500 msec
- ≥ 500 msec
- $30 < \text{change from baseline} \leq 60$ msec
- Change from baseline > 60 msec
- Males: < 450 msec, ≥ 450 msec
- Females: < 470 msec, ≥ 470 msec
- PR interval ≥ 200 msec
- QRS interval ≥ 120 msec

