End of Study (EOS) Date	The EOS date is the date recorded on the eCRF that a randomized subject either discontinued or completed the study. If the subject is lost to follow-up, the EOS date will be the date of the last visit assessment obtained.
Exposure-adjusted incidence rate (EAIR)	EAIR = $100 * 365.25 * (\text{total number of subjects with the AE}) / \text{total exposure time for the selected AE}$ under each

Sponsor: Bristol-Myers Squibb
Protocol no: IM011065

	
treatment that a subject is exposed. Where total exposure time for each AE within a treatment is calculated as follows:
 
• If a subject has at least 1 treatment emergent event while on a particular treatment, then the exposure time for that subject and AE on that treatment is:
◦ First AE onset date – treatment start date (of that particular treatment) +1• If a subject does not have an event, exposure time for that AE is:
◦ Treatment stop date (of that particular treatment) – Treatment start date (of that particular treatment) + 1 + 30 days (if subject discontinued or subject completed but is not rolling into IM011075 study)◦ Treatment stop date (of that particular treatment) – Treatment start date (of that particular treatment) + 1 (if subject completed and is rolling into IM011075 study) 
Total exposure time = sum of exposure time for each AE within a treatment

First Dose Date – Study	The date a subject received their first dose on Day 1 as recorded in the eCRF Week 0 [redacted] dosing date or the earliest drug dispensation date.
Last Dose Date – Study	The date of last recorded dose on the End of Treatment eCRF for a randomized subject. If this date is missing, the latest date from the [redacted] exposure page or drug accountability return date will be used.
First Dose Date – Period	The date a subject received their first dose as recorded in the eCRF Week 0 [redacted] dosing date or the earliest drug dispensation date for Treatment Period 1 and the earliest drug dispensation date for Treatment Period 2.
Last Dose Date – Period	The date of the last visit in the periods – 1. If a subject prematurely discontinues study treatment within a period, the date of last recorded dose on the eCRF will be used as the last dose date for the period.

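### The 30-day EAIR tail in SAP 8.1 has no cap at End of Study or death, so a few event-free subjects are credited with days nobody could observe

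*SAP*

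**What the plan says.** SAP 6.2.1 plans EAIRs for treatment-emergent events by system organ class and preferred term. SAP 8.1 defines the person-time for each event and treatment:

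- A subject with the event contributes time from treatment start to first onset.
- An event-free subject contributes treatment stop - treatment start + 1, plus "30 days (if subject discontinued or subject completed but is not rolling into IM011075 study".
- An event-free completer who rolls into the extension study gets no tail.

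The 30 days mirror the TEAE definition in SAP 4.2, "AEs which occur after the first dose of study treatment through 30 days after the final dose of the study treatment". The EAIR rule does not refer to the EOS date, although SAP 8.1 defines that date in the row just above. For some subjects EOS is set by a special rule: "If the subject is lost to follow-up, the EOS date will be the date of the last visit assessment obtained".

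In Protocol 8.2.2, non-serious AE collection runs "until discharge from the study (ie, final study visit for a given subject", while SAEs are to be collected to 30 days after the final dose, or to the end of participation if that is later. On who remains under observation, the Protocol synopsis states: "Subjects who discontinue study treatment early are expected to remain in the study for continued follow-up until Week 52". Protocol 7.2 excepts a subject who "specifically withdraws consent for any further contact with him/her", and Protocol 7.3 provides for the case "If after all attempts, the subject remains lost to follow-up".

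**The concern.** An incidence rate should count only person-time in which an event could have reached the numerator. The tail meets that test for a subject who stops drug and stays in follow-up. It fails for one who leaves the study at or soon after stopping. That subject can contribute no non-serious event after the final visit, yet the denominator still grows by the full 30 days. After a death the extra days are not time at risk at all; the subject is still event-free for every preferred term that had not yet occurred.

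The error has one direction: it lowers the EAIR. What is at stake is the accuracy of a descriptive safety table. AE counts and percentages, the efficacy tests and the multiplicity scheme are untouched.

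**Working it through.** The plan states no EAIR, person-time or dropout figure, so there is nothing to reproduce. The check applies the SAP 8.1 rule to single subjects and then to an arm.

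**Single subjects** (start on Day 1, event-free)

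| Case | Current rule | EOS cap, floored at treatment stop |
|---|---|---|
| Consent withdrawn and drug stopped, Day 56 | 56 + 30 = 86 | 56 |
| Lost; last visit Day 57, last dose Day 70 | 70 + 30 = 100 | 70 |
| Non-rollover completer, last dose Day 364 or 365, Week 56 visit Day 393 | 394 or 395 | 393 |
| Stops drug, followed beyond stop + 30 days | stop + 30 | unchanged |

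A subject who leaves k days after treatment stop (k < 30) is over-credited by 30 - k days. The non-rollover completer is over-credited by 1-2 days at the target visit (1/393 = 0.25%, 2/393 = 0.51% of that subject's time), or by 0-5 days across the ±3-day visit window.

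**Whole arm, rare event**

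Inputs:
- d = share leaving the study at treatment stop. Assumed 2-10%; not in the documents.
- t = day of leaving. Assumed 56; not in the documents.
- T = days for a completer: 364 (52 weeks) or 112 (16 weeks).
- Completers get no tail. Over 52 weeks this means all roll over. At Week 16 it is a further assumption: SAP 8.1 does not say whether a tail applies when placebo ends at the switch, or when data are cut at Week 16 with active drug continuing.

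Mean observed days = T(1 - d) + d·t. Mean excess = 30d. Understatement = 30d / [T(1 - d) + d·t + 30d].

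| T | d | Observed days | Excess | Understatement |
|---|---|---|---|---|
| 364 | 2% | 356.72 + 1.12 = 357.84 | 0.6 | 0.6/358.44 = 0.17% |
| 364 | 10% | 327.6 + 5.6 = 333.2 | 3 | 3/336.2 = 0.89% |
| 112 | 2% | 109.76 + 1.12 = 110.88 | 0.6 | 0.6/111.48 = 0.54% |
| 112 | 10% | 100.8 + 5.6 = 106.4 | 3 | 3/109.4 = 2.74% |

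The day of leaving hardly matters. With T = 112 and d = 10%, t = 28 gives 3/106.6 = 2.81% and t = 84 gives 3/112.2 = 2.67%.

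**Common event.** If 20% have the event, with onset on average halfway through exposure, only 80% can receive a tail and observed time falls to 0.8 + 0.2 × 0.5 = 0.9 of its former value. The excess is multiplied by 0.8/0.9 = 0.889. Understatement becomes 0.15-0.79% over 52 weeks and 0.48-2.45% in Weeks 0-16, so the rare event is the upper end.

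**Wider assumption.** With 5-20% leaving at mid-period in arms of 146 and 73, the understatement is 1.3-5.8% in Weeks 0-16 and, in the active arm, 0.4-1.8% over 52 weeks. The documents support neither range over the other.

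**The case against.** The strongest defence is that a flat tail matching the TEAE window is a simple convention and almost everyone's tail is observed. Discontinuers are expected to stay to Week 52. Note a to Protocol Table 3 requires the Week 52 assessments, which include AE assessment, from anyone leaving the study early. Protocol 7.1.2 encourages an early-termination visit and the safety follow-up visit. SAEs are to be collected for the full 30 days. All of this stands, and it reduces the problem to mainly non-serious events in subjects who withdraw all contact, are lost or die within 30 days of stopping. It does not remove it: an exit visit held at treatment stop leaves the following 30 days unobserved, and subjects who refuse contact or cannot be found attend no later visit.

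Materiality is also a fair objection. At the upper figure above, a rate of 5.00 per 100 person-years would be shown as 5.00 × (1 - 0.0274) = 4.86. One event more or fewer matters more.

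A reader might infer that, for symmetry, the numerator should be cut off at EOS too. The documents do not support that. SAEs within 30 days of the last dose are to be collected even after the last visit, SAP 4.2 makes them treatment-emergent, and SAP 6.2.1 specifies EAIRs for treatment-emergent events. Cutting them would break agreement with the AE tables. Losing one of five such events would lower that EAIR by about 20% (1/5), far more than the cap raises it.

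The floor at treatment stop can be criticised for keeping Days 58-70 of the lost subject, which no visit covers. That is true, but those are days up to "The date of last recorded dose on the End of Treatment eCRF for a randomized subject". An EOS cap alone would give 57 days and delete 13 on-drug days. The point here concerns only the added tail.

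**Conclusion.** The point holds as a minor one. That the rule lacks a cap is plain from the text; how much this matters is not known. On the assumptions stated, EAIRs are understated by about 0.2-0.9% over 52 weeks, and by about 0.5-2.7% in Weeks 0-16 if Week 16 completers receive no tail.

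Three stronger readings should be resisted. The 30-day tail is not itself wrong, since it matches the TEAE window. Treatment discontinuers in general are not over-credited; only those who leave observation within 30 days are. Nor do the documents show a distorted comparison between arms. If 20% of placebo and 5% of active subjects left at mid-period in Weeks 0-16, the active-to-placebo rate ratio would rise by about 4.8%; with the shares reversed it would fall by about 4.2%. Nothing in the documents gives or suggests such an imbalance.

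**What to change.** In the EAIR row of SAP 8.1, for event-free subjects who discontinued or completed without rollover, end exposure at the earlier of (a) treatment stop + 30 days and (b) the EOS date, or the date of death if the subject died, but never before the treatment stop date. State that the numerator is unchanged: all TEAEs count, including SAEs learned of after EOS with onset within 30 days of the last dose, with exposure running to onset. Leave the TEAE definition in SAP 4.2 and the no-tail rule for rollover completers as they are.

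The cost is one or two lines of SAP text and a small programming change, using dates already collected. No new data and no protocol amendment are needed. With the numerator fixed, affected EAIRs can only rise slightly.

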8.2 Calculation of Key Measures

The following efficacy assessments will be used to assess subjects' disease activity and severity during the study. Outcomes are reported via an eCOA tool at various times throughout the study as described in the protocol Schedule of Activities. At study visits, assessments by the investigator or subjects and results/responses will be reported directly into the eCOA tool at the time of the visit. The tool will open assessments in a sequential manner, meaning that the full assessment is to be completed prior to moving forward to the next assessment. This limits the possibility of partially missing data. Also, as investigators/subjects are prompted to enter data for each assessment for the visit, the possibility of a full assessment being missing is also negated.

Scoring of assessments where validated algorithms are not required will be derived in SAS datasets.

Scoring of assessments where validated scoring tools are required, licenses for these tools will be purchased and used for scoring prior to incorporating into the SAS datasets.

8.2.1 Investigator-Administered Assessments

Assessments will be performed by a qualified physician or dermatologist or trained designee who is experienced in the assessment of psoriasis patients. To limit variability, every effort will be made so that the same individual conducts the assessment at all subsequent visits.

8.2.1.1 static Physician's Global assessment (sPGA)

The sPGA is a 5-point scale of an average assessment of all psoriatic lesions based on erythema, scale, and induration. The sPGA measure determines psoriasis severity at a single point in time (without taking into account the baseline disease condition) as clear (0), almost clear (1), mild (2), moderate (3), or severe (4). A higher score equates to higher severity of disease.

The individual scores at each visit for erythema (E), induration (I) and scaling (S) will be captured via the eCOA system. Scores will range from 0 to 4. A total score will also be computed based on the average of the 3 characteristic scores.

$$\text{Total average score} = \frac{E + I + S}{3}$$

The total average score will be calculated in the eCOA system. The average score will be rounded to the nearest whole number. For example, if the total average score is ≤ 1.49 the score will be rounded to 1. If the score is ≥ 1.5 the score will be rounded to 2. The primary endpoint is derived from the total average score.

sPGA 0 is derived as the binary indicator for sPGA from the calculation above equal to 0 or not; sPGA 0/1 is derived as the binary indicator for sPGA from the calculation above is less than 2 or not;

All individual scores and total average score assessed at each week throughout the study will be transferred to [REDACTED] for analysis. The endpoint derivations will be performed in the analysis datasets.

8.2.1.2 Psoriasis Area and Severity Index (PASI)

The PASI is a measure of the average redness, thickness, and scaliness of psoriatic skin lesions (each graded on a 0–4 scale; 0 = none to 4 = very severe), weighted by the area of involvement

Sponsor: Bristol-Myers Squibb
Protocol no: IM011065

(head, arms, trunk to groin, and legs to top of buttocks). The PASI produces a numeric score that can range from 0 to 72, with higher PASI scores denoting more severe disease activity. The PASI includes multiple subscores and a final total score that will be provided by the eCOA system. Individual plaque characteristic rating scores are provided for each body region as well as the weighted score. Additionally, the degree of involvement of each body region is assessed and that score is multiplied by the weighted plaque characteristic score for a final score for each body region. The total PASI score is a sum of the 4 body regions: Head, Upper Extremities, Trunk and Lower Extremities.

The PASI Total score will be used to assess response to treatment. The percent change from baseline will be calculated at each visit. The PASI 75 endpoint is the proportion of subjects who experience at least a 75% improvement in PASI score as compared with the baseline value.

$$1 = If \left(\frac{\text{Baseline PASI} - \text{Visit PASI}}{\text{Baseline PASI}} \right) \times 100 \geq 75 \text{ then subject is a PASI 75 responder}$$

0 = otherwise

The PASI 50, PASI 90, and PASI 100 are defined similarly. The endpoint derivations will be performed in the analysis datasets.

